The women with PCOS will be stratified according to whether they are insulin resistant or non insulin resistant based upon the results of their glucose tolerance test. Both groups will be randomized to receive the drug flutamide 125 mg/day or placebo. Subjects will take the drug/placebo every day for 6 - 28 day cycles and will continue to take the drug/placebo until all post treatment assessments are completed. Subjects will be asked to collect and store a urine sample once a week during the 6 - 28 day cycles. Subjects will also be asked to complete diaries. Once a month while they are taking the flutamide/placebo, they will return to the clinic and bring their urine samples. At that time they will undergo a physical exam, toxicity assessment, and blood draw. Quality of Life surveys will be performed at baseline, midpoint, and end of study for PCOS participants. Non-PCOS participants will complete Quality of Life surveys at baseline only.

After the 6 - 28 day cycles are completed the PCOS participants will continue to take study drug/placebo until they have completed end of treatment evaluations which include physical exam, additional blood tests, removal of abdominal fat, trasvaginal ovarian ultrasound, MRI, DXA scan, frequently-sampled intravenous glucose tolerance test (FSIGT), and follicle stimulating hormone stimulation test.

Per amendment #11 submitted 11-25-13, subjects who previously underwent an OGTT will be asked to undergo an FSIGT. Women enrolled on the PCOS arm may choose to decline the FSIGT and will undergo an OGTT post treatment.

Per Amendment #24 submitted 6/10/15, we requested permission to add a Family History Questionnaire to this study. Subjects who have been enrolled in the past as well as future participants will be asked to complete the questionnaire. Active study participants will be asked to complete the questionnaire at their next regularly scheduled study visit. Those who have completed all of their study visits will be contacted by phone or email to ask if they will complete the questionnaire. If they agree, it will be sent to the participant by US mail with a stamped return envelope or the questionnaire will be completed over the phone. New study participants will be asked to complete the questionnaire at their eligibility visit. If any participant(s) decline, their participation in Revised 3-7-18 UCLA IRB #12-001780 Page 3 of 27

this study will not be affected nor will their future healthcare at UCLA.

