iii). Body fat distribution: Total body DXA will measure abdominal fat (i.e., the area between the dome of the diaphragm [cephalad limit] and the top of the greater trochanter [caudal limit]). Total body DEXA images also will determine % body fat; fatfree body mass; total body, abdominal, and leg fat; and abdomen/leg fat mass ratio. The leg region is that area below the top of the greater trochanter. Multiple axial abdominal and pelvic MRI slices from the diaphragm to the pelvis will assess cross-sectional areas of SC abdominal and visceral fat.

iv). Ovarian testing:

a). Ovarian morphology: TVUS using a 4- to 8-mHz vaginal probe will be performed in the follicular phase in controls and during amenorrhea in PCOS women. Summed ovarian volume will be calculated. Antral follicle number, defined as the total follicle number (2-9 mm in diameter) of both ovaries, will be determined by 1 investigator ([name]). Polycystic ovaries will be defined by 12 or more follicles in each ovary measuring 2-9 mm in diameter, and/or increased ovarian volume (> 10 ml), with one such ovary sufficient to define PCO.

b). E2 response to recombinant human (rh)FSH. Blood samples will be drawn through an indwelling iv catheter at -90, -60, -30 minutes and time 0 as well as 0.5, 1, 1.5, 2, 3, 4, 6, 8, 10, 12, 16, 20, and 24 h after 150 U rhFSH injection (112). The E2 response to rhFSH will be assessed before and after adjusting for numbers of TVUS-detected ovarian antral follicles.

Aim 2. Examine effect of flutamide in lean PCOS women on SC abdominal adipogenesis, visceral adipose content and ovarian folliculogenesis.

Per amendment #29, we are requesting permission to change the randomization strategy since all PCOS subjects enrolled thus far have been non-insulin resistant

Revised 3-7-18 UCLA IRB #12-001780 Page 7 of 27

based upon the results of the Frequently Sampled Intravenous Glucose Tolerance Test. Therefore, the need to stratify the PCOS subjects into two groups (i.e. insulin resistant versus non-insulin resistant) is unnecessary. All PCOS subjects recruited will now be randomized to study drug versus placebo based upon non-insulin resistant status. Of note, the control subjects are not randomized since they do not receive study drug or placebo.

Adipogenic studies: All adipogenic studies performed at study initiation will be repeated at the end of the 6 - 28 day cycles of flutamide vs. placebo intervention in PCOS women.

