Per amendment #42, epigenetic studies (RNA sequencing, DNA Methylation, and Assay for Transposase Accessible Chromatin Sequencing) on existing fat cell samples will be conducted at UCLA.

INCLUSION CRITERIA

Caucasian and Non-Hispanic women between the ages of 18 to 35 years.

Groups will be: 12 lean controls (Aim 1); 36 age- and BMI-matched PCOS women randomized to flutamide vs. placebo for 6 months (Aims 1 and 2).

i) Lean patients with PCOS: 36 subjects with PCOS (defined by 1990 NIH criteria [all Aims]), BMI 18.5-25 kg/m2. This BMI range is defined as normal and has been chosen to examine underlying mechanisms of PCOS-related androgen excess in the genesis of adipogenic and ovarian dysfunction, independent of obesity. Excessive course hair on upper lip, chin, chest, upper back, lower back, upper abdomen, lower abdomen, arm and/or thigh.

ii) Lean control women: 12 healthy subjects, BMI 18.5-25 kg/m2. Controls will have regular menstrual cycles, and no evidence of hirsutism, acne, alopecia, polycystic ovaries, and/or endocrine dysfunction. This BMI range has been chosen to match that of the PCOS group.

Up to 70 lean PCOS patients and 20 lean controls will be recruited, for a total of 90 study participants over a 5-year interval, accounting for a 20% rate of patient drop-out or insufficient adipose procurement. Participants must be fluent in English.

EXCLUSION CRITERIA

Exclusion criteria for study participation are: present or past history of smoking within past 1 year, cancer, alcohol abuse within past 5 years, drug addiction within past 5 years, severe depression within past 5 years, or post traumatic stress disorder within

Revised 3-7-18 UCLA IRB #12-001780 Page 10 of 27

past 5 years; diabetes; uncontrolled hypertension (≥ 165/100); clinically significant hepatic or renal disease, or other major medical illness; recent (within 3 months) use of androgens, anabolic steroids or hormonal agents (including birth control pills or insulin sensitizers), Mirena IUD, or Plan B contraception. These exclusion criteria are chosen to avoid effects from medical conditions, environmental factors or exogenous agents. Women taking the drug warfarin, beta blockers, CYP active medications, or herbs will be excluded.

Since this study involves MRI testing, women with pacemakers, metal implants, or claustrophobia will be excluded.

The screener will assess the participants response to establish if depression or drug use exclude participation in this study.

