We will use one-way factorial analysis of variance (ANOVA) methods to compare continuous outcomes including hormone levels; adipocyte size, lipid content and glycerol release; numbers of ASCs and preadipocytes; mRNA levels. If data are not normally distributed on any scale, we will carry out nonparametric ANOVA.

Our previous comparison of cFOS gene expression in PCOS women vs. controls showed an increase in Δ Ct (6.0 ± 1.4). Based on this, we hypothesize that the mean difference between controls and IR PCOS is 1.7 SD units. Assuming this, a sample size of 8/group (IR vs. non-IR PCOS) provides over 80% power using the usual two-sided p < 0.05.

We also will compare all outcomes before vs. after 6 months of placebo or flutamide treatment controlling for IR status, using either the parametric paired t test or non-parametric Wilcoxon signed rank test. Insulin action and sensitivity will be assessed by calculating a Matsuda Index from blood glucose and insulin levels during the oral glucose tolerance test. Ovarian estradiol sensitivity to FSH will be calculated from the 24-hr area-under-the-curve (AUC) serum estradiol response to FSH infusion.

Based on our in vitro data, we observed a mean 0.17 log scale change in Δ Ct PPAR γ (SD=0.26 log units) after treatment with T + Flutamide vs. T alone. A sample size of 14 (7 non-IR, 7 IR) provides more than 80% power for the IR adjusted mean change.

REFERENCES

3. 2004. Revised 2003 consensus on diagnostic criteria and long-term health risks related to polycystic ovary syndrome. Fertil Steril 81(1):19-25.

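### The insulin-resistance strata removed by amendment #29 survive in the Lay Summary, the Aim 2 analysis and both sample sizes, and the new rule is unclear on a later insulin-resistant woman

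*Combined protocol and SAP*

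**What the plan says.** The 3-7-18 version treats insulin resistance in four places.

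- **Lay Summary.** "The women with PCOS will be stratified according to whether they are insulin resistant or non insulin resistant", using the glucose tolerance result. Then: "Both groups will be randomized to receive the drug flutamide 125 mg/day or placebo".
- **Research Design and Methods, Aim 2, per amendment #29.** The reason given for changing the randomization is that "all PCOS subjects enrolled thus far have been non-insulin resistant". It follows that "the need to stratify the PCOS subjects into two groups (i.e. insulin resistant versus non-insulin resistant) is unnecessary". The new rule is: "All PCOS subjects recruited will now be randomized to study drug versus placebo based upon non-insulin resistant status".
- **Inclusion and Exclusion Criteria.** The PCOS group is "36 subjects with PCOS (defined by 1990 NIH criteria [all Aims]), BMI 18.5-25 kg/m2". The metabolic part of the exclusion list reads "past 5 years; diabetes; uncontrolled hypertension (≥ 165/100); clinically significant hepatic or renal disease, or other major medical illness". Insulin resistance is neither required nor excluded.
- **Statistical Considerations.** Outcomes are compared "before vs. after 6 months of placebo or flutamide treatment controlling for IR status". The first power statement uses 8 women per group, IR against non-IR PCOS, at a difference of 1.7 SD. The second uses 14 women, 7 non-IR and 7 IR.

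**The concern.** The amendment changed the randomization in one section and left the sections that depended on the old scheme as they were. Two things are at stake.

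First, the stated Aim 2 analysis and both sample sizes assume two IR classes, while the plan reports that only one had been seen. An adjustment for a factor with a single level is empty, and a sample size for a comparison with an empty group supports nothing.

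Second, the new rule opens by covering every recruited PCOS woman and closes by tying randomization to non-IR status. The amendment's reason refers only to women enrolled to date, and no section says what is done with an IR woman found later. The FSIGT follows the eligibility visit (Procedures), so her status becomes known only after she is in the study. Staff should not have to settle her randomization case by case after baseline testing.

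**Working it through.** **1. The sections side by side**

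| Section | IR strata? | Who is randomized |
|---|---|---|
| Lay Summary | Yes, two | Both strata |
| Aim 2 methods (amendment #29) | No | All recruited PCOS women, with a qualifying phrase on non-IR status |
| Inclusion/Exclusion Criteria | Not mentioned | No IR condition |
| Statistical Considerations | Adjusts for IR; 8 vs 8 and 7 + 7 | Assumes IR women are present |

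**2. The plan's own figure.** Inputs from Statistical Considerations: difference 1.7 SD, 8 per group, two-sided 0.05. The noncentrality is 1.7 / √(1/8 + 1/8) = 1.7 / 0.5 = 3.4 on 14 degrees of freedom. Power is 88.5% by the noncentral t, or Φ(3.4 − 1.96) = 92.5% by the normal approximation. The stated figure of over 80% reproduces.

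**3. The same comparison on the plan's own enrolment account.** With zero IR women, the term 1/n(IR) has no finite value. The contrast cannot be estimated, so it has no power. As a conditional illustration only, take 36 PCOS women in all and the same 1.7 SD. Power would be 37%, 62%, 78% and 88% with 1, 2, 3 and 4 IR women.

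**4. What the IR adjustment does.** Write each woman's change as D = μ + β·IR + error. If IR = 0 for everyone, its column is all zeros and β cannot be estimated. The estimate of μ is the plain mean change, with standard error s/√n on n − 1 degrees of freedom. That is the unadjusted paired t test. With exactly one IR woman, the indicator would simply fit her own value.

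**5. Cost of a continuous covariate.** Write D = μ + γ(S − mean S) + error, where S is baseline insulin sensitivity. This leaves n − 2 degrees of freedom. The plan's standardized change is 0.17 / 0.26 = 0.654. Suppose S explains nothing, so that only the lost degree of freedom counts (two-sided t):

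| n | Noncentrality 0.654·√n | Power, n − 1 df | Power, n − 2 df |
|---|---|---|---|
| 14 (the plan's figure) | 2.45 | 61.9% | 61.3% |
| 18 (half of 36, assuming equal arms) | 2.77 | 74.4% | 74.0% |

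The loss is 0.6 and about 0.3 percentage points. On this paired-test reading, the 14-woman figure falls short of the stated 80%. That is a separate matter from the IR leftovers, and it is shown here only because the table needs the baseline.

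**6. The closing phrase.** It can mean (a) that only non-IR women are randomized, or (b) that everyone goes on one list because all were found to be non-IR. The opening words, the stated reason and the absence of any IR criterion favour (b). The phrase adds nothing under (b), which is why it invites (a).

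**The case against.** The best defence is that precedence is visible. The Aim 2 text names itself as the later change and is the methods section; the Lay Summary is plainly out of date elsewhere too, giving 70 participants where the methods and eligibility sections give 90. A careful reader would follow the amendment and randomize without strata. An adjustment that does nothing also biases nothing. This stands, and it settles that the strata are gone. It does not repair Statistical Considerations, where the stated analysis and both sample sizes still rest on the removed classes, and it does not clarify the closing phrase.

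Three stronger inferences are tempting, and the documents do not support them.

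- *That an IR woman's entry to the trial depends on which section is followed.* The amended rule covers all recruited PCOS women, states no exclusion, and the eligibility lists contain none. Because the FSIGT follows the eligibility visit, she would already be enrolled and would count for Aim 1. Only her randomization is unclear, and only on the strained reading (a).
- *That women who kept a baseline OGTT cannot be placed under the amended rule.* The switch to FSIGT dates from November to December 2013. Amendment #24 was submitted in June 2015, so #29 came later if amendments are numbered in sequence. With treatment lasting six 28-day cycles, OGTT-only women had very probably been randomized well before a rule that looks forward.
- *That the number of IR women still to come can be projected.* The plan does not say how many PCOS women had been enrolled when it reported none IR. Any projection would rest on an assumed count.

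**Conclusion.** The point holds as an incomplete amendment. Current text in the Lay Summary and Statistical Considerations keeps IR classes that the Aim 2 methods removed, and the closing phrase of the new rule needs clearing up. If no IR woman has been enrolled since, the planned IR adjustment is identical to no adjustment, and the IR versus non-IR comparison that the 8-per-group figure supports cannot be made. The 7 + 7 split likewise describes a sample the trial does not have.

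This rests on the plan's own statement about enrolment up to amendment #29; later enrolment is not reported. It is not evidence of bias or of a wrongly excluded group. It should be corrected because it changes the stated analysis, and because it prevents ad hoc decisions after baseline testing.

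**What to change.** Use one rule throughout: every eligible PCOS woman is randomized to flutamide or placebo from a single unstratified list, whatever her glucose tolerance result.

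- **Lay Summary:** delete the stratification sentence and reword the next one, which refers to both groups.
- **Aim 2 methods:** delete the closing phrase about non-IR status.
- **Statistical Considerations, analysis:** replace control for IR status with adjustment for continuous baseline insulin sensitivity from the FSIGT. Name the index in advance, since the section at present describes only an OGTT-based one. The paired t and signed rank tests take no covariate, so state the linear model for change that carries it.
- **Statistical Considerations, OGTT-only women:** state their handling before analysis. For example, keep them in the unadjusted comparison, leave them out of the adjusted one, and report their number.
- **Statistical Considerations, sample size:** remove the IR/non-IR splits and restate what the numbers are meant to support.

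The eligibility criteria already fit this rule. The cost is wording in three sections, a changed covariate and one degree of freedom. A few women may lack a common insulin-sensitivity measure, and there would be slight heterogeneity if an IR woman is enrolled. No new data collection is needed, because the baseline FSIGT is already part of the protocol.

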The purpose of this research study is to collect specimen samples and study medical information from women with PCOS and women without PCOS. The goal is to learn more about the changes that take place in the body that result in PCOS.

Revised 3-7-18 UCLA IRB #12-001780 Page 4 of 27

Our Aims are to:

Aim 1: Compare differences in SC abdominal adipose structure-function and regional abdominal adipose content in lean PCOS women vs. age- and BMI-matched controls. Hypothesis: SC abdominal adipose storage is constrained in lean PCOS women.

• Analyze adipocyte size, lipid accumulation, function and secretion of adipokines.

• Analyze same parameters indicated above and signaling pathways in new adipocytes originated from isolated adipose stem cells.

• Use cell culture to examine interactions between adipose stromal-vascular cells and adipocytes in the control of adipose development.

• Correlate key factors with insulin action in vivo; regional and percent body fat; circulating lipids, free fatty acids (FFAs), sex steroids, and adipokines; and ovarian volume, antral follicle number and serum AMH as well as serum E2 response to recombinant human (rh)FSH per antral follicle.

Aim 2. Examine effect of flutamide on SC abdominal adipose structure-function, regional abdominal adipose content and ovarian folliculogenesis in lean PCOS women. Hypothesis: SC abdominal adipose storage is normalized in lean PCOS women receiving flutamide.

• Examine in vitro effects of sex steroids on adipogenesis.

• Determine changes in SC abdominal adipogenesis, circulating lipids, FFAs, sex steroids, and adipokines.

• Determine changes in SC abdominal and visceral adipose content, fat free mass as well as percent body fat.

• Determine changes in ovarian morphology and function as well as ovulatory frequency, as measured by weekly urinary pregnanediol glucuronide (UPDG).

• Determine key factors that predict ovulation by serial urinary UPDG measurements.

RESEARCH DESIGN AND METHODS

Aim 1. Compare differences in SC abdominal adipogenesis of lean PCOS women vs. age- and BMI-matched controls

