Procedures: All procedures performed at study initiation also will be repeated at the end of the 6 - 28 day cycles of flutamide vs. placebo intervention in PCOS women. The end of treatment fat biopsy will be performed of the opposite side of the lower abdomen than where the first biopsy was taken. In addition, monthly liver function studies will be performed to detect possible elevations of serum transaminase levels above the normal range during flutamide vs. placebo therapy.

Menstrual records and urinary pregnanediol glucuronide (UPDG): Ovulatory frequency will be determined by having subjects keep a daily menstrual record and collect weekly first morning urine samples for UPDG and creatinine assay. Urine samples will be stored for later analysis. Urine samples will be analyzed at the University of Wisconsin-Wisconsin National Primate Research Center for the urinary metabolite of progesterone (urinary pregnanediol glucuronide [UDPG]) and creatinine testing.

Six months following the completion of protocol procedures, participants who received flutamide/placebo will be contacted by phone to check on the status of their health. Subjects will be asked if they have experienced any health problems or have become pregnant since they completed the study procedures.

Daily diaries will include self reporting on taking pills, menstrual flow, symptoms, concomitant medications, exercise patterns, and diet habits.

Quality of life assessments and ovarian size measurements will be conducted at baseline, and at the end of 3 and 6 months of treatment. The PHQ, Beck's Anxiety, Beck's Depression questionnaires will be completed at baseline. The Beck's Depression and Beck's Anxiety will be completed at 3 and 6 month visits. Scoring of the Quality of Life surveys (Beck's anxiety and Beck's depression questionnaires) will be at the time the subject is present for their study visit. If any areas of concern are identified, they will be addressed with the subject before they leave and the appropriate referrals

Revised 3-7-18 UCLA IRB #12-001780 Page 8 of 27

will be made.

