The study procedures will take place at UCLA Westwood Campus in the 200 and 300 Medical Plaza Buildings, the Clinical Translational Research Center, Ronald Reagan Medical Center, and/or Room 22-265 in the Center for Health Sciences.

Before subjects begin the study:

Before they begin the study, subjects will need to agree to use a non-hormone type of

Revised 3-7-18 UCLA IRB #12-001780 Page 12 of 27

birth control for the duration of their participation in this study. If subjects have not undergone permanent sterilization, examples of acceptable types of birth control are an IUD (without hormones) or spermicidal jelly in combination with a diaphragm or condoms.

During the study:

If subjects take part in this study, the researcher(s) will ask them to do the following:

All Study Participants

Initial Visit

• The consent form will be reviewed with the subject and anyone they wish to have present. If they choose to participate, they will sign the consent form and HIPAA Authorization form. Subjects will be given a copy for their records.

The doctor will ask questions regarding their past medical history, family medical history, and lifestyle to determine if they are eligible to participate in this study.
If subjects are not eligible to participate in this study, no further study related office visits or procedures will be performed and they will receive \$10 for their time
If subjects are eligible to participate, they will undergo the following:

- Physical Exam
- An assessment of their skin
- Height, weight, waist and hip measurements
- Transvaginal ultrasound of their ovaries
- Blood tests approximately 1 teaspoon (6 ml) of blood will be drawn from their vein. All of the blood samples in this study will be used to detect any abnormal hormone levels. A pregnancy test will also be performed.
- Complete questionnaires regarding their feelings about various areas of their health, quality their life, and family history of PCOS and/or diabetes. Subjects have the right to refuse to answer any questions that they do not wish to answer.
- \circ Whether subjects are eligible or not, they will be paid \$20 for completing this visit.
 - It is estimated that this visit will take approximately 2 hours.

Women with and without PCOS

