• Complete a diary regarding what time they took the pill, whether they had any menstrual bleeding, any changes in their health, any medications they took, if they exercised that day, and a brief summary of their diet.

• Collect a sample of their first morning urine once a week and store it until their next clinic visit. Subjects will be given instructions on the collection and storage of the samples.

• Return to the UCLA Clinic once a month for the following:

o A brief physical exam including a measurement of their height, weight, waist, and hips. Review any symptoms subjects may have experienced during the past month.

o Bring their prescription bottles so that the pills can be counted.

o Bring their weekly urine samples.

o Bring their completed diaries.

o Have blood tests (serum pregnancy test, complete blood count, and comprehensive metabolic panel) – approximately 1 teaspoon (5 ml) of blood will be drawn.

o After the third and sixth cycle, subjects will be asked to complete questionnaires regarding their feelings about various areas of their health and the quality of their life. Subjects have the right to refuse to answer any questions that they do not wish to answer. • After the third and sixth cycle, subjects will also have an assessment of their skin, and a transvaginal ultrasound of their ovaries.

• It is estimated that each of these visits will take approximately 1 hour

• Subjects will receive be reimbursed for their parking expenses and receive \$240after all 6 visits have been completed.

• Subjects will be asked to continue taking the flutamide or placebo until the procedures listed below are completed. Every effort will be made to complete all study visits as soon as possible.

After Completing Flutamide/Placebo

The FSIGT, MRI, DXA, Removal of Abdominal Fat, and FSH tests will be repeated as described above. Please note that a testosterone blood test, complete blood count, and comprehensive metabolic panel will be performed at the post-treatment FSH test.

30 Days after Last Pill

o Physical Exam

o Blood tests (pregnancy test, complete blood count, and comprehensive metabolic panel) - approximately 1 teaspoon (6 ml) of blood will be drawn from their vein.

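### Ovarian ultrasound, skin and Beck scores are scheduled at month 3, but the planned paired test gives month 3 no role and omits women without a month-6 value

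*Combined protocol and SAP*

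**What the plan says.** The schedule is explicit.

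- Research Design and Methods, Aim 2, Procedures: "Quality of life assessments and ovarian size measurements will be conducted at baseline, and at the end of 3 and 6 months of treatment". On the questionnaires it adds: "The Beck's Depression and Beck's Anxiety will be completed at 3 and 6 month visits". Baseline completion is given just before that.
- Procedures, list for women with PCOS: "After the third and sixth cycle, subjects will also have an assessment of their skin, and a transvaginal ultrasound of their ovaries".
- Procedures, Initial Visit: the baseline list includes "An assessment of their skin", an ovarian ultrasound and questionnaires.

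Aims and Objectives makes the ultrasound relevant to Aim 2: "Determine changes in ovarian morphology and function as well as ovulatory frequency". Skin and Beck scores are not named in the aims. They enter the analysis only because it covers all outcomes.

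Statistical Considerations gives one analysis for the treatment period: "We also will compare all outcomes before vs. after 6 months of placebo or flutamide treatment controlling for IR status". The method is a paired t test, with the signed rank test as its nonparametric alternative. In the text supplied, that section names no repeated-measures model, no use for month 3, no analysis population and no rule for missing data.

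**The concern.** A paired t or signed rank test needs both members of a pair. With baseline and month 6 as the pair, the month-3 value has no place, and a woman measured at month 3 but not at month 6 contributes nothing.

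Two things are at stake. The first is bias. Completer pairs represent the randomised arm only if loss is unrelated to outcome. The protocol's own rules tie some losses to what happens on treatment. Rules for Withdrawing Participants lists liver tests above normal, pregnancy and a persistent rise in blood pressure. Potential Risks has study drug discontinued at grade 3 toxicity. The reproductive-risk text says flutamide can occasionally induce ovulation, so a pregnancy withdrawal could be linked to ovarian response itself. A likelihood-based model that includes month 3 needs a weaker condition: loss may depend on values already observed and modelled.

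The second is precision. In a trial expecting 36 PCOS completers, a scheduled measurement on an Aim 2 outcome should not be left without an analysis.

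**Working it through.** **1. The plan's own figure for the paired test.** The documents give no figure for the month-3 outcomes. The only figure for a paired comparison is for PPARγ expression: mean change 0.17, SD 0.26, 14 women, power above 80%. The standardised change is 0.17/0.26 = 0.654. A two-sided 5% paired t test with n = 14 then has 61.9% power, so the figure does not reproduce unless the insulin-resistance adjustment cuts the SD to about 0.21. This is a separate matter and nothing below depends on it.

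**2. Inputs for the precision check.**

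- PCOS completers: 36 (Aim 1, Subjects and clinical assessment). At 1:1, which is assumed because the ratio is not stated, c = 18 per arm.
- Loss: 20% (Inclusion Criteria). Starters = 36/0.8 = 45, or 22.5 per arm, so 4.5 per arm are lost.
- Timing of loss: not stated. Taken as half to all after month 3, so women per arm with a month-3 value are m = 18 + 2.25 = 20.25, or m = 22.5.
- Correlations: not stated. Assumed 0.6 between baseline and each later visit, and 0.7 or 0.8 between months 3 and 6.

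**3. Correlation of months 3 and 6 given baseline.** r = (ρ − 0.6²)/(1 − 0.6²).

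- ρ = 0.7: r = 0.34/0.64 = 0.531, r² = 0.282.
- ρ = 0.8: r = 0.44/0.64 = 0.688, r² = 0.473.

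**4. Variance of the month-6 arm difference**, mixed model divided by baseline-adjusted completer analysis: 1 − r²(m − c)/m.

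| Losses after month 3 | (m − c)/m | ρ = 0.7 | ρ = 0.8 |
|---|---|---|---|
| Half | 2.25/20.25 = 0.111 | 0.969 | 0.947 |
| All | 4.5/22.5 = 0.200 | 0.944 | 0.905 |

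Variance falls by about 3 to 10%. Dividing 18 by these ratios gives 18.6 to 19.9 effective women per arm, a gain of about 0.6 to 1.9.

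**5. Bias, illustrated.** A simulation took 22 starters and 18 finishers per arm and a true difference of zero. In one arm only, women with changes at one end of the month-3 range were more likely to be lost. Here the correlation is between the month-3 and month-6 changes, set from 0.3 to 0.9. The completer difference was 0.07 SD at 0.3, rising to 0.20 SD at 0.9. Because the other arm is unaffected, the same shift appears in the within-arm mean change that the plan tests. Using month 3 brought it to 0.00 to 0.01 SD. This drop-out pattern is assumed. It shows how large the effect could be and does not predict it.

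**The case against.** Several objections have weight.

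- **The plan does not say month 3 is discarded.** Correct: it is silent. A reader might infer that the month-3 data are wasted, but for the Beck scores that is not so. They are scored at the visit, and concerns are dealt with before the woman leaves. What is missing is a role in the analysis.
- **Stopping the pills is not the same as missing month 6.** This also stands. The documents do not say whether women who stop treatment are still measured, so the point is limited to women with no month-6 value.
- **The loss may be small.** A reader might subtract 36 completers from the 70 PCOS women to be enrolled and conclude that 34 could have month-3 data only. With 17 more women per arm, ρ = 0.8 gives 1 − 0.473 × 17/35 = 0.77, a 23% fall in variance. The documents do not support this. Consent precedes the eligibility assessment, and the baseline tests precede the first pill, so some of the 34 would never reach month 3. Inclusion Criteria also gives 70 as a ceiling and states a 20% loss. Even that rate includes inadequate fat samples, which do not affect these outcomes.
- **The ratios are not measured against the plan's test.** True. They compare two analyses of the arm difference, whereas the paired test is within-arm. The missing flutamide-placebo comparison is a separate and larger problem, which the same model would address.
- **Month-3 content is uncertain.** Neither antral follicle number nor mFG score is named at month 3. Ultrasound in PCOS women is meant to be done during amenorrhea, yet the monthly blood tests include no progesterone. Comparability across visits, and so the assumed correlation, is open.
- **A Gaussian model loses the Wilcoxon fallback.** Fair for bounded, possibly skewed scores; the fix has to cover it.

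None of this supplies an analysis for the month-3 ultrasound.

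**Conclusion.** The point holds as a minor improvement to the analysis. A named Aim 2 outcome and two others are scheduled at three time points, and the only stated test uses two of them and women with both values.

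Possible bias is the stronger reason to change, because some withdrawal rules respond to on-treatment results. The mixed model does not remove all of it: if loss depends on something outside the model that also relates to outcome, bias remains.

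The precision gain is secondary: about 3 to 10% of the month-6 variance, under the stated correlations, 1:1 allocation, 20% loss and half to all of it after month 3. If losses come earlier or the correlations are weaker, it is smaller. A reader might also look for a gain from averaging months 3 and 6 when nobody drops out, but neither the plan nor the recommended contrast uses that average.

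The reach is narrow. The fat biopsy, MRI, DXA, FSIGT and FSH-test outcomes are measured only at the start and end of treatment, and ovulation rests on weekly urine samples.

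**What to change.** For ovarian volume and Beck scores, and for antral follicle number and mFG score if they are recorded at month 3, replace the paired test by a mixed model for repeated measures:

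- terms for arm, visit (months 3 and 6), arm-by-visit and baseline value;
- all randomised women with at least one post-baseline value;
- the month-6 arm difference as the main contrast;
- unstructured 2×2 covariance with a small-sample degrees-of-freedom correction;
- the missing-at-random assumption stated in the plan;
- a transformed or rank-based sensitivity analysis for skewed scores.

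State which ultrasound and skin variables are recorded at month 3. State also whether women who stop study drug are still measured at month 6.

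The cost is revised analysis wording and a little more analysis work, with no new visits or samples. The downside is reliance on missing-at-random, which the data cannot verify.
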